9.4 Definition of Populations

The population will be 232 postmenopausal women, age 18 or older. For more detailed description of the study population see *Section 4. SELECTION AND ENROLLMENT OF PARTICIPANTS*.

9.5 Interim Analyses and Stopping Rules

No interim analyses of primary or secondary data are anticipated.

This study will be stopped prior to its completion if:

- In the opinion of the DSMB and IRB, the intervention is associated with adverse effects that call into question the safety of the intervention.
- If there are life-threatening SAEs that are related or potentially related to the study intervention the DSMB would discuss the risk of the intervention to the subjects and make a recommendation on continuation of the study.
- Recruitment or retention becomes untenable to the extent that study end point data collection is not possible.
 - The two PIs will meet at least monthly (and more frequently if needed) to review accrual goals. Should the situation arise that one site recruits more quickly than the second site (to the extent that the ability to meet accrual goals appear endangered), the Co-PIs will confer to increase accrual efforts at that site. Should these actions fail to produce the anticipated and necessary results for the site, the Co-PIs will confer with the NCCIH Program Officer (PO) and DSMB to request approval for increased accrual at the other site.
- New information becomes available during the trial that necessitates stopping thetrial;

• Other unanticipated problems or situations occur that might warrant the IRB, DSMB, or NCCIH stopping the trial.

9.6 Outcomes

9.6.1 Primary Outcome

Hot flash score: Hot Flash Daily Diary

A Hot Flash Daily Diary will be used to measure the primary outcome of hot flash score. Participants will be asked to complete the Hot Flash Daily Diary every day for 6 weeks to measure the daily frequency and severity (mild, moderate, severe, and very severe) of hot flashes. Each level of severity is given a value; mild = 1; moderate = 2; severe = 3; very severe = 4. Participants will rate the severity of each hot flash as they experience it and record it in their daily diary. A total hot flash score will be calculated for each participant (product of frequency x severity). For example, a woman with 3 mild and 2 severe hot flashes would have a hot flash score of 9 (3x1 = 3 + 2x3 = 6). Participants are educated on how to collect hot flash information in real time throughout the course of each day.

9.6.2 Secondary Outcomes

Hot flash activity interference: Hot Flash Related Daily Interference Scale (HFRDIS)

Participants will be asked to complete the Hot Flash Related Daily Interference Scale (HFRDIS) during baseline and weeks 6 and 12. This is a 10 item scale that measures hot flash interference.^[82] The HFRDIS asks respondents to rate the degree on a 0-10 scale that the hot flashes interfere with various daily activities as well as overall enjoyment or quality of life. This measure has been shown to be valid and internally consistent, with an alpha of .96.^[82] Individual items and a total summary score will be used.

Anxiety: PROMISTM Emotional Distress – Anxiety Scale

The PROMISTM Emotional Distress – Anxiety Scale contains 29 items that measure 5 domains of anxiety: 1) affective, 2) cognitive, 3) somatic, 4) behavioral, and 5) need for treatment. Items are scored on a scale from 1-5 with higher scores reflecting more severe anxiety. Like all PROMIS measures, the anxiety scale was developed through rigorous qualitative and quantitative assessment involving expert review, focus groups, and item response theory analysis, and it has shown excellent convergent and discriminate validity with other measures, with a Cronbach's alpha of .95.^[83, 84]

Sleep disturbance: Pittsburg Sleep Quality Index (PSQI)

The PSQI is a 19-item self-report inventory designed to measure sleep quality. The 19 items are grouped into 7 subscales: 1) sleep quality; 2) sleep efficiency; 3) daytime dysfunction; 4) sleep latency; 5) sleep disturbances; 6) sleep duration; and 7) use of sleep medication. These seven subscales are scored on a scale of 0-3 with higher scores indicating greater sleep pathology. Previous studies indicate that PSQI total scores are significantly correlated with measures of sleep onset latency, amount of time spent awake after initial sleep onset, and total sleep time as assessed by sleep diary and wrist actigraphy,[85] and alphas for the PSQI range from .70 to .80.^[86] A cut point of 5 has been determined through evidence to differentiate sleep disturbance (≤5) from normal sleep. [87]

Perception of benefit: Subject Global Impression of Change

The Subject Global Impression of Change is a 7-point item in which the participant rates the change in hot flashes since beginning the study (ranging from "very much better," "moderately better," "a little better," "about the same," "a little worse," "moderately worse," to "very much worse"). It has been used extensively for determination of minimally clinically significant differences in numerous oncology clinical trials. [88, 89] Four additional investigator-developed

questions will be included, of those four, two will be about satisfaction..

Diurnal Cortisol Rhythm

Each participant will be provided a kit with salivettes for the collection of saliva. Saliva will be collected three times a day over a two-day period. Participants will be provided specific directions for the collection of saliva upon awakening, (before getting out of bed), 30 minutes later (before eating, drinking or tooth brushing), and finally at bedtime (around 10 pm, also before tooth brushing) and will be given a Saliva Collection Diary with questions to answer surrounding their saliva collection. (This procedure is well established and is considered valid for the measurement of diurnal cortisol rhythm. [67, 68]

Measures of Heart Rate Variability

The shift in autonomic balance from sympathetic dominance (stress response) to parasympathetic dominance (relaxation response) is a very likely candidate for the underlying mechanism of the effects of mind-body interventions on vasomotor symptoms. Relatedly, an increasing body of evidence indicates that hot flash events are associated with changes in heart rate variability. Polar V800, a mobile HRV recording device will be worn to collect data over a 24-hour natural ambulatory period as well as two supine standardized 6-minute recordings. The 24-hr and 6 min measurements will be completed (each on separate days) at pre- and post-trial. The ambulatory device will be returned to the investigators and downloaded for optimal resolution and to protect privacy. The Polar V800 has been shown to have equivalency for the time domain of HRV.

Perceived Stress Scale (PSS)

The PSS contains 10 items that measure the degree to which situations in one's life are appraised as stressful. [94] The scale provides the degree to which individuals find their lives to be

unpredictable, uncontrollable, and overloaded, as well as measures the current levels of experienced stress.^[95] Items are scored on a scale from 0-4 with higher scores reflecting more perceived stress. This measure has been shown to be valid and internally consistent, with an alpha of .83.^[94]

[name] Hypnotizability Scale (EHS)

The EHS is a 12-item, research assistant-administered, scale for rating hypnotizability in the general population. Each item is rated pass\fail, with higher scores indicative of greater hypnotizability.

Previous research indicates that the EHS is highly correlated with longer measures of hypnotizability and has excellent reliability with a Cronbach's alpha of .94.^[96]

Self-Hypnosis Practice Log

Frequency of home practice is thought to be one of the moderators of the efficacy of hypnosis interventions^[70] and will be particularly important to collect for this self-administered protocol.^[70] Participants in both groups will be given a log that they will complete daily. The log will provide space to put the date, whether or not the participant listened to their audio recording, the number of times they practiced (with and without the audio recordings), and provide a space for comments about any interruptions or barriers to listening to their assigned recording. Between the log and the phone calls, the research assistant will be able to ascertain the degree to which women adhered to the protocol in terms of recording hot flashes in real time and using the audio-recordings as prescribed in the protocol.

9.7 Data Analyses

In general, we will conduct an intent-to-treat (ITT) analysis in which all participants randomized to a treatment condition will be analyzed as such regardless of noncompliance, withdrawal, etc. A common strategy for ITT analysis when participants withdraw from a study is to carry the last observation forward. Given the likely underestimation of the variability due to that approach, we will employ multiple imputation to address missing data. We will also analyze the data based on completers and for those who have primary endpoint data at 6 weeks. We will explore the differences in the outcomes; and also explore which characteristics are present in those who do and do not have primary endpoint data. (See section 9.6, missing data).

Objective #1

The primary outcome will be change in hot flash scores over time during the treatment weeks (Weeks 1-6) compared to baseline between groups. Seven hot flash scores will be used (i.e., baseline score + weekly score for weeks 1 through 6) for each group. Hot flash scores will be used as the dependent variable in a longitudinal regression model that accounts for both group assignment as well as changes across the seven measurement points. The effective number of observations for this model is 1,624 observations (232 participants × 7 hot flash scores = 1,624). A second model will be constructed to include the week 12 (follow-up) data, which is an 8th observation for each participant to evaluate treatment sustainability as a secondary outcome. The effective number of observations for the model is 1,856 observations (232 participants × 8 hot flash scores = 1,856). The effect of the hypnosis intervention will be determined in these models by the difference between the changes hot flash scores (i.e., slopes) between the hypnosis and control groups. Important potential confounder variables (e.g., race/ethnicity, education, etc.) can easily be included in these models to account for their effects. The model described above is shown algebraically below.

```
Level 1 Model:
Y_{ti} = \pi_{0i} + \pi_{1i} a_{ti} + e_{ti}
Y_{ti} = Hot flash score at time t for participant i
\pi_{0i} = Intercept (average) hot flash score at baseline
\pi_{1i} = Amount of change in hot flash score associated with time t
a_{ti} = Value of time t
e_{ti} = Random error in hot flash score at time t for participant i [e_{ti} \sim N(0, \sigma^2)]
Level 2 Model:
\pi_{0i} = \beta_{00} + \beta_{01} X_1 + r_{0i}
\pi_{1i} = \beta_{10} + \beta_{11}X_1 + r_{1i}
\beta_{00} = Grand mean hot flash score at baseline for control group
\beta_{01} = Expected difference in hot flash score at baseline between treatment and control groups
X_1 = Value of Treatment indicator (X); 0 = control, 1 = treatment
\beta_{10} = Average amount of change in hot flash score across time for control group
\beta_{11} = Difference in amount of change in hot flash score across time between treatment and control group
r_{0i} = Random error of intercept for participant i adjusted from group assignment [r_{0i} \sim N(0, \tau_{00})]
r_{1i} = Random error of amount of change for participant i adjusted from group assignment [)]
[r_{1i} \sim N(0, \tau_{10})]
Combined (Mixed) Model:
```

The effect of primary interest is the interaction between time and treatment, which is the $\beta_{11}X_1a_{ti}$ term.

 $Y_{ti} = \beta_{00} + \beta_{01}X_1 + \beta_{10}X_1 + \beta_{11}X_1a_{ti} + r_{1i}a_{ti} + r_{0i} + e_{ti}$

Objective #2

Secondary outcomes (activity interference from hot flashes, sleep disturbance, stress, and anxiety) will be entered separately as dependent variables into a similar type of longitudinal regression model described above. The primary difference in models is that for the secondary objectives, one set of models will be estimated using data collected at two points (i.e., baseline & week 6) and another set of models will be estimated using data collected at three time points (i.e., baseline, week 6, & week 12 [follow-up]).

Objective #3

The focus of Aim #3 is to determine the extent to which cortisol levels, HRV, and perceived stress mediate the relationship between group assignment and hot flashes. For each, we will test the null hypothesis that there is no mediation, or indirect effect, of these potential mediators on the hot flashes although we hypothesize that the relationship between group assignment and hot flashes will be mediated by these variables. Measurement considerations are presented for cortisol levels and HRV followed by a description of the mediation analysis plan. Cortisol levels will be evaluated using a commercial immunoassay with chemiluminescence detection by the CLASS lab at the University of Michigan for all samples from Baylor and Michigan. The lower concentration limits are 0.44 nmol/liter with intra- and interassay coefficients less than 8%. Cortisol slopes will be determined by recording cortisol values at three different times of day for each of the two collection days at baseline and at the end of the intervention, week 6. Higher slope values will reflect flatter diurnal cortisol rhythms. If values are found to be non-normal, we will use log transformations. [99] For HRV, we will extract beat-to-beat (NN) intervals from the recordings collected by the Polar S810. From these, we will use the well-validated Kubios HRV analysis software package[100] to calculate time domain indices of parasympathetic activity (standard deviation of NN intervals, SDNN; and root mean square of standard deviation

of NN intervals, RMSSD) according to standard guideline.^[101] These measures cover both short and longer term recordings and will be collected at baseline and the end of the intervention, week 6.

Mediation analysis will be performed using a nonparametric bootstrap method, to determine how much of the improvement in the primary and secondary outcomes is mediated by psychophysiological effects of the intervention and by changes in perceived stress. The nonparametric bootstrap method provides more statistical power than traditional mediation analysis and does not require the assumption of normality. Within-subject change in HRV, cortisol slopes and perceived stress scores will be tested as mediators. Average causal mediation effects (ACME) and average direct effects (ADE) will be calculated to compare the mediated and un-mediated portion of the changes in the primary and secondary outcomes between groups. We will also test if pre-trial HRV predicts treatment effects, as we expect that women with high SNS activity at baseline will have the most to gain.

Moderator analysis will be performed using the longitudinal regression models described above. The benefit of using the longitudinal regression model for examining moderation is that the unique contribution of each moderator to the variability between people/groups or to the variability across time can be determined.

Missing Data

Based upon our previous research (R34 AT008246-03) we anticipate minimal missing data on the primary outcome (hot flash scores) and drop-outs of 18% or less of those that start treatment; and the specific pattern of missing data found in our prior study was primarily toward the end of data collection. Therefore, in the present study some missing data is anticipated, particularly at follow-up (week 12). Our statistician has advanced experienced in R, Mplus, and SAS packages and has focused training in missing data analysis in Mplus and SAS. To handle missing data we will follow Little's (1995) recommendation by collecting multiple pieces of evidence for the tenability of missing completely at random (MCAR) assumption if we experience substantial (e.g., > 5%) missingness. That is, as appropriate we will (a) conduct Little's (1988) test of missing completely at random using the observed data as input, (b) test the equality of the distributions of each of the outcome measures with missing data patterns using t test for location, (c) compute the standardized mean difference in each of the outcome measures across missing data patterns, and (d) examine the distribution of demographic variables across missing data patterns. If the possibility of systematic bias is present, we will most likely consider a multiple imputation method using Mplus or SAS. Again, our statistician has experience and coding knowledge to conduct the analyses in either package. Additionally, we will collect multiple pieces of information that allow us to assess the extent to which excluding those who did not complete the entire protocol may introduce systematic bias. We note that missing data in longitudinal data collection studies has been referred to by Little and Rubin^[102] and Schafer and Graham^[103] as "monotone" because the missingness tends to appear toward the end of data collection rather than the beginning (as we anticipate based upon our prior studies). When the attrition mechanism does not depend on observed or unobserved outcome variables, the pattern can be described as completely random drop-out^[104] which is a special case of Rubin's^[105] MCAR assumption.^[106] We acknowledge that a standard mixed-model analysis or the use of HLM package will not handle different patterns of missing data on the six weeks of hot flash diaries or home practice logs. As noted, our statistician has experience and coding knowledge to conduct analysis in R, Mplus, and SAS packages and has focused training in missing data analysis in Mplus and SAS.

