Based on previous studies, the mean hot flash score for post-menopausal women selfadministering hypnosis is about 23 with standard deviation of 10.9. We simulated 10,000 data points from a normal distribution with mean of 23 and standard deviation of 7; we used a smaller standard deviation because the standard deviation from the previous pilot was based on a small sample. Next, we simulated a 50% reduction in hot flash scores for the 5,000 simulated values to mimic the expected effect self-administered hypnosis post treatment. We also simulated a 25% reduction in hot flash scores for the other 5,000 simulated values to mimic the expected effect of the selfadministered sham white noise hypnosis at the post treatment data point. The hot flash distribution for the simulated self-administered hypnosis condition at the post treatment data point had mean of 11.4 (SD=9.8) whereas the distribution for the simulated structured attention condition at post treatment had a mean of 17.2 (SD=9.9). These effects represent a strictly standardized mean difference of .41 between the self-administered hypnosis and structured attention conditions. We used the strictly standardized mean difference in lieu of the traditional standardized mean difference because it is slightly more conservative to ensure sufficient power. The strictly standardized mean difference in the reduction rates, when taking group variability into account, of 0.41 was entered into G*Power and Optimal Design software. Using a Type I error rate (α) of 5% and power of 80%, the required sample size is 190 without attrition in both power analysis programs. Because the withinbetween interaction for two time points (i.e., baseline and follow-up) is equivalent to an independent samples t test on the difference scores, Power was computed in the G*Power using the t distribution for independent samples on the difference scores. We entered the effect size of .41, Type I error rate of 5%, Power of 80%, and N2/N1 ratio of 1 (i.e., balanced design). The required sample size was 190. Power was cross-validated in the Optimal Design software using the Person Randomized Trial Design with Single Level Trials (i.e., participants are the experimental units). Using Type I error rate of 5% and effect size of .41, the required sample size was 190. Given the expected attrition rate of 18% attrition or less, the sample size required to accomplish all aims of this study is 232 participants. We should note that the framework described above for determining power generalizes to objective #2 and the moderator analysis described in objective #3. The power analysis should also be sufficient for the mediation analysis.

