
Treatment Assignment Procedures

Enrolled participants will be randomized to either self-administered hypnosis or self-administered sham white noise hypnosis. Randomization will be accomplished by the statistical team with the development of two case assignment spreadsheets; one for each site, thus assuring equal treatment arms by site. Randomization will be accomplished by the statistical team using stratified permuted block randomization with fixed blocks of size four. Two strata will be used: site (University of Michigan or Baylor University) and participant subgroup (post-menopausal or breast cancer). All randomization block permutations will be generated, and one permutation will be

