randomly assigned to each block. Given that block size will be fixed at four, there are six permutations of randomization. One of the six permutations will be randomly to each block of participants. The randomization information will be printed on individual cards (e.g., "46BRG32: Self-Administered Hypnosis Group" or "46BRG32: Self-Administered Sham White Noise Hypnosis Group"), each of which will be placed in a brown security envelope and sealed (one card per envelope). It is expected that each site (Baylor University and University of MI) will each randomize approximately half of the participants, but each site will receive two sets of 116 envelopes – one set of 116 for each participant subgroup. It is not expected that there be an equal distribution of participants who are post-menopausal or breast cancer survivors; rather, the randomization strategy ensures an equal distribution of each subgroup into the self-administered hypnosis intervention or self-administered sham white noise hypnosis condition regardless of the proportion of each participant subgroup within site. For example, if Baylor University randomizes 100 participants who are post-menopausal and 16 who are breast cancer survivors, having two sets of 116 randomization envelopes ensures that (1) there are enough envelopes and (2) there are 50 post-menopausal and 8 breast cancer survivors in each condition. Therefore, one set of sealed envelopes for post-menopausal participants with group assignment and one set of sealed envelopes for breast cancer survivors with group assignment will be provided to both [name] team and [name] team. The case assignment spreadsheets will be kept by the statistician, and not accessible to persons who will be educating, obtaining consent from the participants, collecting data, or interacting in any other capacity which involves contact with participants, as this may possibly cause bias in the recruitment process. All participants randomized will be included in the analyses (i.e., intent-to-treat analysis).

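### The primary model omits the randomisation strata (site and participant subgroup); if they predict change in hot flash score, the test is mildly conservative

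*Combined protocol and SAP*

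**What the plan says.** Section 3 and section 9.3 (Treatment Assignment Procedures) describe stratified permuted blocks of fixed size four. On the factors, section 9.3 says: "Two strata will be used: site (University of Michigan or Baylor University) and participant subgroup (post-menopausal or breast cancer". The stated purpose is balance within each subgroup: "the randomization strategy ensures an equal distribution of each subgroup into the self-administered hypnosis intervention".

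Section 9.7, Objective #1, writes out a two-level growth model with a random intercept and a random slope. The Level 2 equations for intercept and slope each contain one covariate, X1, defined as "Value of Treatment indicator (X); 0 = control, 1 = treatment". The effect of primary interest is the time-by-treatment term, β11. The only statement about other covariates is permissive: "Important potential confounder variables (e.g., race/ethnicity, education, etc.) can easily be included in these models to account for their effects". Site and subgroup are not among its examples.

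Objective #2 carries the same structure over to the secondary outcomes, which "will be entered separately as dependent variables into a similar type of longitudinal regression model described above". Nothing in the text reviewed commits to either stratification factor as a model term, alone or by time.

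**The concern.** By stratifying, the plan treats site and subgroup as factors worth balancing, but the analysis then ignores them. If either factor is related to how much a woman's score changes, balancing it makes the treatment contrast more precise than simple randomisation would. A model without the factors leaves that variation in the residual slope variance. Its standard error is then too large and its test rejects less often than 5% under the null. What is at stake is lost efficiency and confidence intervals slightly wider than they need to be. It is not a question of bias or false positives.

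A second, separate point is that an optional covariate list ending in an open et cetera leaves the final form of the primary model to the analyst. The calculations below do not measure that.

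**Working it through.** **Inputs from section 9.3.** Effect size 0.41, alpha 5%, power 80%, 1:1 allocation, 190 women before attrition, 18% attrition, 232 in total; four strata (2 sites × 2 subgroups), blocks of four. Power came from an unadjusted comparison: "Power was computed in the G*Power using the t distribution for independent samples on the difference scores".

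**Assumed input.** R², the share of variance in change explained by the strata. The documents do not give it, so the range 0 to 10% is shown.

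**Step 1: the plan's own figure.** A two-sample t test with d = 0.41, two-sided alpha 0.05 and power 0.80 needs 94.35 per arm, rounded up to 95, so 190 in total. Then 190 / (1 − 0.18) = 231.7, rounded up to 232. Both figures are reproduced. The plan does not state sidedness; a one-sided test would need 148, so the plan's figure is two-sided. Power at 95 per arm is 80.3% by the t distribution and 80.7% by the normal approximation used below.

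**Step 2: link to the primary model.** With complete, balanced data, the test of β11 in the random-slope model is the same as a two-sample t test on each woman's fitted slope. The calculation for a t test on change therefore carries over.

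**Step 3: formulas.** Under stratified blocking the true variance of the treatment contrast is (1 − R²) times the variance that the unadjusted model reports. Write s = √(1 − R²) and δ = 0.41 × √(190/4) = 2.826.

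- Overstatement of the standard error: 1/s − 1
- True alpha, unadjusted: 2 × (1 − Φ(1.96/s))
- Power, unadjusted: Φ((δ − 1.96)/s)
- Power, adjusted: Φ(δ/s − 1.96)
- Equivalent N: the N that solves 0.41 × √(N/4) − 1.96 = δ − 1.96 × s

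Example at R² = 5%: s = 0.9747. The overstatement is 1/0.9747 − 1 = 2.6%. Alpha is 2 × (1 − Φ(2.011)) = 4.4%. Unadjusted power is Φ(0.866/0.9747) = Φ(0.888) = 81.3%. Adjusted power is Φ(2.899 − 1.96) = Φ(0.939) = 82.6%.

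| Assumed R² | SE overstated | True alpha | Power, unadjusted | Power, adjusted | Gain (points) | Equivalent N |
|---|---|---|---|---|---|---|
| 0% | 0% | 5.0% | 80.7% | 80.7% | 0 | 190 |
| 2% | 1.0% | 4.8% | 80.9% | 81.4% | 0.5 | 192.7 |
| 5% | 2.6% | 4.4% | 81.3% | 82.6% | 1.3 | 196.7 |
| 10% | 5.4% | 3.9% | 81.9% | 84.6% | 2.7 | 203.8 |

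The gain is worth about 0, 3, 7 or 14 extra women.

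**Step 4: simulation check.** This used 20,000 trials per setting, 232 women and blocks of four, with equal strata (58 each) or strata of 100/16/100/16, and with or without 18% random dropout. Type I error of the unadjusted test was 4.8–4.9% at R² = 0, 4.4–4.6% at 5% and 3.9–4.0% at 10%. With site and subgroup in the model it was 4.8–5.2% throughout (R² up to 20%). A separate run of 12,000 trials per setting at N = 190, assuming 30% in the breast cancer subgroup, gave power gains of 0.0, 0.5, 1.3 and 3.0 points for the four rows of the table. The mean estimate was about 0.41 with and without adjustment, so there is no bias.

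**Step 5: where the terms must go.** The growth model was fitted to 300 simulated trials with 18% dropout. With site and subgroup in the intercept equation only, the standard error of β11 was 1.000 times the unadjusted one. The unadjusted standard error was 1.045 times the one from a model with the terms in the slope equation as well.

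**The case against.** The strongest reply is that nothing fails. The test is valid, it matches the unadjusted t test used for sizing, and the planned power is reached. That is correct, and it is why this is an improvement rather than an error.

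The upper end of the range is also demanding. With R² = 10% split equally, each factor explains 5%. Two equal-sized sites would have to differ in change by √0.05/0.5 = 0.45 SD, and the subgroups by √(0.05/0.21) = 0.49 SD if 30% are breast cancer survivors. With the 16-of-116 example in section 9.3, the subgroup difference would be about 0.65 SD. All of these exceed the planned treatment effect of 0.41. Section 2.2 also reports similar reductions in hot flash score with hypnosis in the two populations: 71.36% at week 6 in general-population women and 68% in breast cancer survivors. These percentages come from different trials with different controls and give no R², but they suggest a small subgroup effect.

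Finally, 0.41 is a strictly standardised difference. The simulated means and SDs in section 9.3 give an ordinary standardised difference of 5.8/9.85 = 0.59. At that value, unadjusted power at 190 is about 98% and the gains are only 0.08, 0.19 and 0.33 points at R² of 2%, 5% and 10%. Those are post-treatment SDs; the SD of change is not given.

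These arguments make the likely gain smaller. They do not change the direction, the omission itself, or the negligible cost of correcting it.

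**Conclusion.** The point holds. The plan stratifies by site and subgroup and does not require either in the primary or secondary models. The consequence is conditional and mild: none if the strata do not predict change, and at an assumed R² of 10% a standard error 5.4% too large and 2.7 points of power forgone. Indirect evidence in the documents favours the lower part of the range. These sizes rest on the assumed R², on 0.41 being taken as the standardised effect on change, and on a two-sided test. Strata that predict only the baseline level do not matter for the slope test when data are complete. The sample size does not need to change.

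**What to change.** In section 9.7, add site and participant subgroup as fixed effects to both the Level 2 intercept equation and the Level 2 slope equation, which means site-by-time and subgroup-by-time terms (or stratum-by-week terms if week is treated as categorical). Apply this to the primary and the secondary longitudinal models. State that this is the single pre-specified primary model, and move race/ethnicity, education and any other covariates to a sensitivity analysis with a closed list.

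The cost is one or two sentences and a few degrees of freedom out of about 190 to 232 women. Both variables are already recorded for randomisation.

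### The combined equation for the primary model puts the control group's time coefficient on treatment instead of time, contradicting the plan's own level equations; separately, the covariance of the random intercept and slope is not stated

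*Combined protocol and SAP*

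**What the plan says.** Section 9.7, Objective #1, models seven weekly hot flash scores per woman (baseline and weeks 1 to 6).

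- Level 1: "Y_{ti} = \pi_{0i} + \pi_{1i} a_{ti} + e_{ti}", so time multiplies the participant's slope.
- Level 2, intercept: "\pi_{0i} = \beta_{00} + \beta_{01} X_1 + r_{0i}".
- Level 2, slope: "\pi_{1i} = \beta_{10} + \beta_{11}X_1 + r_{1i}".
- beta10 is defined as "Average amount of change in hot flash score across time for control group".
- beta11 is defined as "Difference in amount of change in hot flash score across time between treatment and control group".
- Combined line, the fixed terms after beta00: "\beta_{01}X_1 + \beta_{10}X_1 + \beta_{11}X_1a_{ti}".
- Test: "The effect of primary interest is the interaction between time and treatment".

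The random intercept is normal with variance tau00. The random slope, "Random error of amount of change for participant i adjusted from group assignment", is normal with a variance written tau10. No joint distribution or covariance is given. Objective #2 and the moderator analyses reuse the same kind of model.

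**The concern.** There are two separate issues.

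First, the combined line is the form a programmer would turn into mixed-model code, and it is not the model that the level equations define. Its beta10 term is zero for every control, although beta10 is defined as the controls' change. Section 9.3 expects a 25% fall under sham. With no control time trend in the model, that fall would be counted as treatment effect.

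Second, the plan does not say whether intercept and slope may correlate. If they are fitted as independent when higher-scoring women in fact fall faster, the standard error of the primary contrast is too small.

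**Working it through.** **1. Substitution.** Put the two Level 2 equations into Level 1, writing X for treatment and a for time:

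Y = (beta00 + beta01·X + r0) + (beta10 + beta11·X + r1)·a + e

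= beta00 + beta01·X + **beta10·a** + beta11·X·a + r0 + r1·a + e

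The combined line agrees in every term except one: it has beta10·X in place of beta10·a.

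**2. Consequences of the printed line.** Its fixed-effect columns are 1, X, X and X·a. That is four columns with rank 3, because beta01 and beta10 share a regressor and only their sum can be estimated. If the duplicate is dropped, controls have a mean of beta00 at every week. The hypnosis arm keeps its own intercept and its own slope, so with complete data beta11 equals that arm's slope.

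**3. Size.** Inputs from section 9.3: baseline mean 23, reductions of 50% (hypnosis) and 25% (sham). Linear change over six weeks is assumed.

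- Hypnosis slope: -23 × 0.50 / 6 = -1.917 per week
- Sham slope: -23 × 0.25 / 6 = -0.958 per week
- Correct beta11: -1.917 - (-0.958) = -0.958
- Printed line's beta11: -1.917, twice the correct value

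Simulated trials (232 women, seven weeks, 60 trials per scenario) agree. The printed line averaged -1.89 to -1.92 and the level equations -0.94 to -0.96. With both arms falling 25%, so that the true difference is zero, the printed line averaged about -0.95 to -0.96 and rejected in 60 of 60 trials. The level equations averaged about zero and rejected in 3% to 8%, including the fits without a covariance.

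**4. The unstated covariance.** Assumed, since the plan gives no variance components: intercept SD 6.3, slope SD 1.0, residual SD 3.1. At baseline this puts 6.3² / (6.3² + 3.1²) = 39.69 / 49.30 = 81% of the variance between women, in line with the plan's figure of nearly 80%.

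The true standard error of beta11 with 116 per arm and complete data, where the squared deviations of weeks 0 to 6 sum to 28, is

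sqrt(2 × (1.0² + 3.1² / 28) / 116) = sqrt(2 × 1.343 / 116) = 0.152

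This does not depend on the correlation. The standard error reported by a model that forces independence does. In large samples its type I error is 2 × [1 - Φ(1.96 × sqrt(R))], where R is the ratio of model-based to true variance:

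| True correlation | R | Type I error |
|---|---|---|
| -0.5 | 0.876 | 6.7% |
| -0.3 | 0.930 | 5.9% |
| 0 | 1.00 | 5.0% |
| +0.3 | 1.06 | 4.4% |
| +0.5 | 1.10 | 4.0% |

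At -0.5 the reported standard error is 0.152 × sqrt(0.876) = 0.142, about 6% too small. In the simulated trials, omitting the covariance left the estimate of beta11 unchanged to three decimals.

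**5. Which sign do the documents suggest?** In the earlier data quoted in section 9.3, the hypnosis-arm spread fell from 1.02 at baseline to 0.56 at week 12. With independent random effects the variance at time a is tau00 + a²·tau11 + sigma², which cannot fall, so this points to a negative covariance. The evidence is mixed, however: the control-arm spread rose from 1.23 to 1.36.

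**6. Sample size.** A two-sided t test (sidedness assumed) with d = 0.41, alpha 5% and power 80% gives 95 per arm, or 190 (power 80.3%). Then 190 / (1 - 0.18) = 232. Both stated figures reproduce. They rest on difference scores, so neither issue touches them.

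**The case against.** The strongest reply is that the right model is already in the plan. The level equations, the definitions of beta10 and beta11, and the prose on slopes and on the group-by-time interaction all agree. One symbol in a derived line departs from them, and its rank deficiency would expose the slip. The equation block also shows signs of damage in PDF reading, with a stray bracket beside the slope variance and the equation standing after the sentence that refers to it. A lost or altered symbol cannot be excluded. All of this stands.

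A reader might infer that the whole primary model is mis-specified and that a false positive is near certain. The documents do not support that. The 60 of 60 rejections arise only if someone drops the duplicated column and ignores everything else in the section.

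A reader might also infer that the covariance must be negative because the reductions are planned as percentages of baseline. The planning figures do not show this. Starting from SD 7, proportional falls within each woman would give post-treatment SDs of 7 × 0.50 = 3.5 and 7 × 0.75 = 5.25. The plan reports 9.8 and 9.9, which match change independent of baseline: sqrt(49 + 49) = 9.90. Nor does giving two separate normals fix the covariance at zero; it is simply not stated.

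**Conclusion.** The combined equation is wrong as printed and contradicts the level equations and the definition of beta10. Read literally, it doubles the planned effect, from -0.96 to -1.92 points per week, by counting the sham response as benefit. The error lies in that line and not in the intended model, and it is subject to a check of the source PDF.

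The missing covariance is a separate and smaller matter. It changes the standard error, not what beta11 estimates. Under the assumed variance components, fitting independent random effects gives a type I error of about 6% to 7% at correlations of -0.3 to -0.5, and below 5% if the correlation is positive. A negative correlation is plausible from the earlier hypnosis-arm data but not established.

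**What to change.** In section 9.7, after checking the source PDF:

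- In the combined equation, replace beta10·X1 with beta10·a_ti.
- Relabel the slope variance tau11.
- State that (r0i, r1i) are bivariate normal with variances tau00 and tau11 and covariance tau01, estimated freely (unstructured).
- Carry the corrected form into Objective #2 and the moderator models.

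Make the change before the database is locked and allocation is revealed. It costs a few words of SAP text and one extra variance parameter. The sample size does not change.
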